9.6 Analysis of Study Endpoints

Study endpoints will be summarized by treatment group and overall as appropriate. Continuous variables will be summarized by presenting the number of subjects, mean, standard deviation, median, minimum, maximum by procedure group (Study Group or SOC Group). Tabulation of categorical variables by group will include counts and percentages. 95% confidence intervals will be provided as appropriate.

Since this is an exploratory study, additional analyses, additional analysis populations, covariates and

summary tables and/or graphs will be generated as needed.

In all analyses described below, the null hypothesis will be a two-sided test of no treatment group difference. All statistical tests will use a two-sided significance level of $\alpha=0.05$.

9.6.2 Safety Analysis

AEs related to the CryoAnalgesia procedure or device will be reported on the eCRF. These AEs will be listed and descriptively summarized for patients in the Study Group. No formal statistical hypothesis will be tested.

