Adverse Event Assessment: All adverse events shall be recorded in the subject's source documents. Only adverse events that are related to the intercostal analgesia procedure or the AtriCure® cryoICE cryo-ablation system need to be reported on the eCRFs. Refer to description of collection of Adverse Events for additional information.

Allodynia Screening: As part of the 90 and 180 day follow-up visit, a series of questions will be asked of the subject to determine if an in-office visit is necessary to further evaluate the presence of allodynia.

Allodynia Assessment: Cotton Tip Applicator (CTA) Test. See Appendix 2 for instructions. The same person at the site should administer the test at each time point and should be blinded as to treatment group.

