9.5 Analysis Populations

Intent-To-Treat (ITT) Population: The effectiveness, safety and health economics analyses will be based on the ITT population. The ITT Population is defined as all subjects randomized to either the Study Group or SOC Group and on whom the surgical index procedure is attempted (even if the index procedure is aborted).

Per-Protocol (PP) Population: A PP population may be defined for effectiveness and health economics and analyses. This population is defined by ITT population but without any major protocol violations, that is, those that could potentially bias the results.

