10.2.4 Reporting Adverse and Serious Adverse Events

The investigator (or designee) will record all AEs (both serious and non-serious and regardless of relationship) in the source documents. The Investigator at each site participating site is responsible for reporting AEs and SAEs to AtriCure only when they are related to the CryoAnalgesia index procedure or device. AEs related to the CryoAnalgesia procedure or device will be reported on the eCRF. The CRFs allow the investigator to indicate whether or not the adverse events are related to the device or index procedure.

- Use a separate Adverse Event Form to document each event
- The Adverse Event Form must be electronically signed by the Investigator

Note: It is the responsibility of the Investigator to inform their IRB of SAEs as required by their IRB procedures and in conformance with FDA requirements.

All Serious Adverse Events that are related to the CryoAnalgesia index procedure or device must be reported by the Investigator by submitting the AE eCRF to AtriCure within 10 days of becoming aware of the AE. An event determined by the Investigator to be life threatening or to have led to death should be reported within 24 hours.

The Investigator shall send a written report including a narrative description of the SAE to AtriCure within three (3) working days of the initial report. The Investigator should follow all unresolved SAEs

until the events are resolved, or the subject has exited the study or the AE is otherwise explained.

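### Apart from deaths, only adverse events judged related to cryoanalgesia must reach the eCRF, and only the Study Group is summarised, so harms that the thoracotomy can also cause have no planned control-arm rate

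*Combined protocol and SAP*

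**What the plan says.** All references are to the combined protocol and SAP.

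- **Entry on the eCRF.** Section 7.11 has every AE recorded in source documents, but limits eCRF entry: "Only adverse events that are related to the intercostal analgesia procedure" or to the device's "cryo-ablation system need to be reported on the eCRFs". Section 10.2.4 applies the same limit to sponsor reporting: the investigator "is responsible for reporting AEs and SAEs to AtriCure only when they are related to the CryoAnalgesia index procedure or device".
- **Deaths.** Section 10.2.2 requires any subject death to be submitted on the AE eCRF, with no relatedness condition.
- **Summary.** Section 9.6.2: "These AEs will be listed and descriptively summarized for patients in the Study Group". No safety hypothesis is tested.
- **Population.** Section 9.5: "The effectiveness, safety and health economics analyses will be based on the ITT population". That population contains both randomised groups.
- **Index procedure.** Section 5.1 restricts the term to use of the cryoICE system. Section 7.2 uses it more widely and lists the control arm's standard pain management under it.
- **Named harms.** Section 10.0 lists skin injury, intercostal muscle injury and permanent nerve damage as device risks, with numbness, neuralgia and hyperesthesia as possible symptoms. Appendix 3 puts muscle injury and permanent nerve damage in its class above 10%.
- **Two-arm sensory data.** Section 9.6.1 compares allodynia between arms at 3 and 6 months. Both arms are screened first: "a series of questions will be asked of the subject to determine if an in-office visit is necessary".

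**The concern.** The Introduction (section 1.0) says that thoracotomy itself interrupts muscle and neurovascular structures. Both arms have the thoracotomy and only one has the nerves frozen. Numbness round the incision, neuralgia, muscle injury and lasting sensory change may therefore come from the incision, from the cryoanalgesia, or from both. For these events an investigator's judgement of relatedness is at its least reliable, and a randomised control arm is at its most useful.

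The plan relies on the judgement and sets the control arm aside. At stake is whether the study's safety table can be interpreted for the harms that the protocol itself names. Nothing here touches the co-primary analyses of FEV1 and VAS pain.

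**Working it through.** **Step 1. Can a control-arm AE qualify for entry?** Entry requires a relationship to the device or to the cryoanalgesia index procedure (7.11, 10.2.4). Under section 5.1 the index procedure is use of the cryo system, which a control subject does not receive. Non-fatal control AEs therefore fall outside the requirement by construction. Under the wider use in section 7.2, a control event caused by standard pain management might qualify, but one caused by the incision still would not.

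**Step 2. Do other data supply a control rate?** Deaths do (10.2.2). Allodynia does (9.6.1), but the Appendix 2 test records normal sensation or sudden sharpness and has no outcome for numbness. Pain medication, spirometry and shoulder movement are collected in both arms and are only indirect signals. The wording of the allodynia screening questions is not in the text available, so whether they touch on numbness cannot be checked.

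**Step 3. Size of the relatedness filter.** The plan gives no safety figure to reproduce. Its planned group sizes (section 9.3) are 75 and 25. Assume that 30 of 75 Study Group subjects have numbness and that a share f is judged cryo-related. The reported rate is 30f/75:

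| f | Reported |
|---|---|
| 0 | 0/75 = 0% |
| 0.5 | 15/75 = 20% |
| 1 | 30/75 = 40% |

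**Step 4. What a control rate would add.** The Newcombe 95% interval for d = p1 − p2 uses each arm's Wilson limits (l, u): lower = d − √[(p1 − l1)² + (u2 − p2)²]; upper = d + √[(u1 − p1)² + (p2 − l2)²].

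Example, 30/75 against 3/25: p1 = 0.400 (Wilson 0.297 to 0.513), p2 = 0.120 (0.042 to 0.300), d = 0.280.
- Lower = 0.280 − √(0.103² + 0.180²) = 0.073.
- Upper = 0.280 + √(0.113² + 0.078²) = 0.418 (from unrounded limits).

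The 8/75 rows take the smallest count consistent with Appendix 3's class above 10% (0.10 × 75 = 7.5, so at least 8). All other counts are assumptions.

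| Study Group | Control | Difference (points) | 95% CI |
|---|---|---|---|
| 30/75 | 3/25 | +28.0 | +7.3 to +41.8 |
| 30/75 | 10/25 | 0.0 | −21.9 to +20.1 |
| 8/75 | 0/25 | +10.7 | −3.6 to +19.7 |
| 8/75 | 3/25 | −1.3 | −20.0 to +10.6 |

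The first two rows give the same Study Group figure and opposite readings. Under the present plan they cannot be told apart.

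**Step 5. Precision.** The half-width is 1.96·√[p(1 − p)(1/75 + 1/25)], with an assumed common rate p in both arms:
- p = 0.10: 13.6 points
- p = 0.20: 18.1 points
- p = 0.30: 20.7 points

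**The case against.** The strongest defence is that this is an exploratory post-market study of cleared devices used on label, with no safety hypothesis and with a two-arm allodynia comparison. A listing of device-related events is one-arm by its nature, so it sits less sharply against an ITT safety population than it first appears. With 25 controls and AEs that nobody solicits, a by-arm table would seldom separate cryoanalgesia from incision effects: three of the four intervals above include zero. All of this stands, and it is why the point is only an improvement. It does not remove the gap, because section 9.5 still promises a two-arm safety basis that no planned table uses.

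Three stronger readings are tempting, and the documents do not support them.

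- **Control AEs are lost for good.** They must be in source documents in both arms, those documents are retained, and section 9.7 allows a detailed SAP before database closure. The events could still be abstracted late. What is missing is a planned entry and a planned table.
- **SAE reporting is contradictory.** Section 10.2.4 says: "An event determined by the Investigator to be life threatening or to have led to death should be reported within 24 hours". This follows directly on a sentence confined to related SAEs, and its ordinary reading is a faster clock for that subset. In the Study Administrative Structure section, the wide regulated-product wording can be read as attaching to product use errors and not to SAEs in general.
- **Neuralgia is missed because no visit falls between day 30 and day 90.** Subjects are told to notify the investigator of any AE (section 4.1), and the day-90 call includes an AE assessment (section 7.7). The gap in visits is also the same in both arms, so it does not explain a missing control rate.

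**Conclusion.** The point holds as a gap in AE entry and tabulation. Followed as written, the plan yields a Study-Group-only count, filtered by relatedness, for harms that the incision can also cause. It gives no control rate for numbness, neuralgia, intercostal muscle injury, skin injury or permanent sensory change. Deaths and allodynia at 3 and 6 months are exceptions.

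At the assumed 40% Study Group rate, the unseen excess could be anything from nil to 28 points, depending on a control count that the plan does not collect. Near the protocol's own 10% class, both illustrative intervals include zero, so there a by-arm table would describe and not discriminate. These sizes rest on assumed counts and on the planned 75/25 split. The structural conclusion rests on the text alone.

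This is a cheap improvement in interpretability. It is not a threat to the primary results, and it is not evidence that any harm is being concealed.

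**What to change.** 1. Enter on the eCRF, in both arms and regardless of judged relatedness, all SAEs and the section 10.0 events recorded in source documents: numbness, neuralgia, hyperesthesia, intercostal muscle injury, permanent nerve damage and skin injury.
2. Tabulate these and deaths by randomised arm, with the risk difference and 95% CI, descriptively and without a test. Keep the listing of device-related events.
3. Reconcile section 9.5 with sections 7.11, 9.6.2 and 10.2.4, and section 5.1 with section 7.2 on the meaning of index procedure.
4. Preferably, add yes/no items on numbness and neuralgia to the 90- and 180-day screening questions already put to both arms.

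**Cost.** Extra data entry and coding for up to 100 subjects. Source recording is already required, MedDRA coding is planned (section 8.1.8), and the form already has the field needed: "The CRFs allow the investigator to indicate whether or not the adverse events are related to the device or index procedure".

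**Downsides.** AEs in source documents are unsolicited and partly unblinded, so the by-arm table can be biased. Item 4 reduces that for sensory symptoms only and adds a few minutes per call. Precision stays low, with half-widths of about 14 to 21 points.

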9.7 Detailed Analysis Plan

Prior to looking at the data and database closure, if needed, a detailed statistical analysis plan will be prepared and finalized to completely specify the statistical procedures to be applied to the data by the statistician who will conduct the analysis. The plan will amplify on the methods discussed in this protocol, will address any protocol changes that would affect the analysis, and will provide a rationale for any changes to the analysis.

10.0 Safety Monitoring

Subject safety will be monitored throughout the course of this study by monitoring for Adverse Events and Product Complaints related to the AtriCure *cryoICE* Probe (CRY02) used in conjunction with the *cryoICE* BOX (v6). The AtriCure *cryoICE* Probe (CRY02) used during the index procedure for the clinical study has been cleared for marketing by the FDA and is being used within the current labeling and indications for use. Any event that occurs that may have caused or contributed to a death or serious injury or that indicates the AtriCure *cryoICE* Probe (CRY02) device has malfunctioned and would be likely to cause or contribute to a death or serious injury if the malfunction were to recur will be reported in compliance with 21 CFR Part 803.

In addition to general surgical risks, additional risks specifically associated with the AtriCure *cryoICE* Probe (CRY02) are as follows:

- Skin injury due to cryoablation of skin
- Intercostal muscle injury
- Permanent peripheral nerve damage

These risks could lead to symptoms that include:

- Numbness around the incision lasting from 1 to 6 months
- Neuralgia occurring 6 weeks after cryoanalgesia, lasting up to 2 months
- Hyperesthesia

There may also be other risks that are unforeseen at this time. The complete Risk/Benefit Assessment is found in Appendix 3.

10.1 Adverse Events

10.1.1 Definition of an Adverse Event

Adverse Event (AE): any undesirable clinical occurrence or change from a patient's baseline (pre-index procedure) condition, whether it is device related or not.

Adverse Event Identification: a condition that is one of the following:

- a. A unique symptom or event that is a change from the subject's baseline status
- b. A series of symptoms or events that can be categorized as a single entity based on definitions found herein
- c. A specific diagnosis responsible for a clinical change
- d. A worsening or exacerbation of a pre-existing condition

10.2 Serious Adverse Events

10.2.1 Definition of a Serious Adverse Event

Serious Adverse Event (SAE): any adverse event is considered serious if it results in death, is life threatening, requires hospitalization (initial or prolonged), results in disability or permanent damage, causes congenital anomaly/birth defect, requires intervention to prevent impairment or damage, or other serious (important medical events) which may jeopardize the subject and may require medical or surgical intervention to prevent one of the above outcomes.

Note: "Death" should not be reported as an adverse event. The cause of death should be reported as an

adverse event. The only exception is “Sudden Death” when the cause is unknown.

10.2.2 Subject Death

Subject death during the investigation must be reported by the Investigator (or designee) by submitting the Adverse Event eCRF to the Sponsor, within 24 hours of learning of the adverse event. The electronic Adverse Event Form must be electronically signed by the Investigator. A copy of the death records, death certificates and an autopsy report (if performed) are required to be sent to the AtriCure or designee within 10 days following the death. Any death must be reported to the FDA within 10 working days of AtriCure or designee’s knowledge of the death. In addition, subject death must be reported to the IRB in accordance with IRB requirements.

10.2.3 Adverse Event Classification

The investigator is required to provide:

- Time interval of the event – The time interval of the occurrence of the adverse event should be assessed in relationship to timing of the index procedure (Use of the AtriCure® cryoICE cryo-ablation system)
- Date of event onset and outcome of the event, or date of death
- Severity of the event – (Mild, Moderate, Severe)
- Action taken for medical management of the event

Relationship of the event – it is the PIs responsibility to assess the relationship of an AE and provide primary cause. Events will be categorized by relationship to the AtriCure *cryoICE* Probe (CRY02) device, the *cryoICE* BOX (v6), an ancillary device, the index procedure or other.

- Adverse events will be assessed to determine if the event meets the definition of a serious adverse event.

10.2.4 Reporting Adverse and Serious Adverse Events

The investigator (or designee) will record all AEs (both serious and non-serious and regardless of relationship) in the source documents. The Investigator at each site participating site is responsible for reporting AEs and SAEs to AtriCure only when they are related to the CryoAnalgesia index procedure or device. AEs related to the CryoAnalgesia procedure or device will be reported on the eCRF. The CRFs allow the investigator to indicate whether or not the adverse events are related to the device or index procedure.

- Use a separate Adverse Event Form to document each event
- The Adverse Event Form must be electronically signed by the Investigator

Note: It is the responsibility of the Investigator to inform their IRB of SAEs as required by their IRB procedures and in conformance with FDA requirements.

All Serious Adverse Events that are related to the CryoAnalgesia index procedure or device must be reported by the Investigator by submitting the AE eCRF to AtriCure within 10 days of becoming aware of the AE. An event determined by the Investigator to be life threatening or to have led to death should be reported within 24 hours.

The Investigator shall send a written report including a narrative description of the SAE to AtriCure within three (3) working days of the initial report. The Investigator should follow all unresolved SAEs

until the events are resolved, or the subject has exited the study or the AE is otherwise explained.

11.0 PRODUCT COMPLAINTS

11.1 Medical Device Reporting and Product Complaints

All reported device observations, malfunctions or failures for CryoAnalgesia products will be reported [REDACTED]

Whenever an event involving an AtriCure device is subject to reporting under that Medical Device Reporting (MDR) regulation, AtriCure shall submit to the FDA the appropriate reports required by MDR within the time frames as identified in 21 CFR Part 803. Criteria for reporting malfunctions and potentially serious injuries is based on interpretations of medical intervention, potential for serious injury, and impact of a malfunction to a device's essential functionality. AtriCure will follow - reference documents (QS-007, MDR/Reportable Incident Reporting and QS-006, Complaint Procedure) medical device in compliance with reporting, 21 CFR Part 803 and 21 CFR Part 820: Code of Federal Regulations, Quality System Regulations.

11.2 Source Of Product Complaint Data

Means of obtaining product complaint data include review of the subject's medical records or observation by the PI and/or study staff or the CRA.

13.0 Appendices

APPENDIX 1 - Visual Analog Scale

0–10 Numeric Pain Rating Scale

Mankoski Pain Scale Definitions

- 0- Pain Free
- 1- Very minor annoyance- occasional minor twinges. No medication needed.
- 2- Minor annoyance- occasional strong twinges. No medication needed.
- 3- Annoying enough to be distracting. Mild painkillers take care of it. (Aspirin, Ibuprofen.)
- 4- Can be ignored if you are really involved in your work, but still distracting. Mild painkillers remove pain for 3-4 hours.
- 5- Can't be ignored for more than 30 minutes. Mild painkillers ameliorate pain for 3-4 hours.
- 6- Can't be ignored for any length of time, but you can still go to work and participate in social activities. Stronger painkillers (Codeine, narcotics) reduce pain for 3-4 hours.
- 7- Makes it difficult to concentrate, interferes with sleep. You can still function with effort. Stronger painkillers are only partially effective.
- 8- Physical activity severely limited. You can read and converse with effort. Nausea and dizziness set in as factors of pain.
- 9- Unable to speak. Crying out or moaning uncontrollably- near delirium.
- 10- Unconscious. Pain makes you pass out.

APPENDIX 2 – ALLODYnia ASSESSMENT

Allodynia and *hyperpathia* are terms used to describe the hypersensitivity that occurs with neuropathic pain. Many different techniques have been used to assess skins sensitivity, including alcohol pads, Von Frey fibers, and camel hair brushes (<https://www.youtube.com/watch?v=-eRSx0Cbxks>). Recently, the use of a cotton tip applicator (CTA) has been described to test skin sensitivity to evaluate abdominal wall allodynia due to chronic pelvic pain (1). This simple test has been validated as a reproducible screening method to identify cutaneous allodynia in women with or without chronic pelvic pain (2), and we propose to use this same simple test to evaluate neuropathic pain following chest wall surgery. For a video of the technique used to evaluate chronic pelvic pain, please see <http://www.jove.com/video/1232/demonstration-cutaneous-allodynia-association-with-chronic-pelvic>.

1. An explanation of the test is undertaken and permission to proceed is obtained.
2. The patient exposes the chest wall at the surgical site.
3. A disposable sterile cotton-tipped applicator is shown to the patient and brushed against the patient's hand to demonstrate how the light pressure will feel.
4. The cotton-tipped culture stick is then lightly drawn down the chest wall in the anterior axillary line, the mid axillary line, and the posterior axillary line, as well as the anterior and posterior extents of the incision. The patient is asked to note the point at which light pressure applied to the skin becomes sharp as the cotton-tipped culture stick is drawn down the chest wall, starting approximately 2 rib interspaces above the surgical incision, and continuing at least 3 interspaces below the surgical site.
5. The patient will either note the presence of normal sensation or will note a sudden and discrete sharpness in sensation. A positive test is defined by the presence of this sudden sharp sensation. A small mark with a marking pen will be used to map the border of the area of sensitivity. The process should be repeated until the entire area of cutaneous allodynia has been identified. The furthest "north, south, east and west" points will be marked around the incision. A photograph of the area of sensitivity may be taken to document increasing or decreasing areas of allodynia, but is not required.
6. The north south east and west points will be measured for height and width in centimeters (cm).
7. In some cases the areas are large but in others they will be small. Some areas may encompass the entire length of the incision, while others may involve only a very small, specific site.

1. Jarrell J. Demonstration of cutaneous allodynia in association with chronic pelvic pain. *J Vis Exp.* 2009(28).

